4.5.1. Reasons for Discontinuation and Individual Stopping Rules

Individual Subjects will be discontinued by the Investigator if they meet any of the stopping rules described below:

1. A significant febrile reaction defined as \geq Grade 2 fever (>39.0 °C) associated with systemic symptomatology (eg, body aches, malaise, nausea) within 24 hours following administration of IP.
2. An absolute decrease in predicted FEV1 of at least 25% compared to the baseline value (defined as the average of the Day -1 and Day 1 pre-dose values) during the 5-week treatment period in Part B or through Day 11 (1 week post-5th dose) in Part D that cannot be explained, in the opinion of the PI, by the underlying disease of CF and that is confirmed on 2 separate occasions at least 3 days apart
3. A suspected moderate to severe allergic/hypersensitivity reaction, including but not limited to anaphylaxis, generalized rash, edema or bronchospasm possibly related to drug treatment
4. Deterioration of liver function as explained below and in Section 8.1.4.1
 - a. Elevation of ALT or AST to >5 x ULN in a subject regardless of baseline value
 - b. Elevation of ALT or AST to >3 x ULN in a subject with a normal baseline or elevation of >3 x ULN from the subject's actual baseline if not normal, with the

appearance of fatigue, nausea, vomiting, right upper quadrant pain or tenderness, fever, rash, and/or eosinophilia (>5%).

c. Elevation of ALT or AST to >3x ULN in a subject with a normal baseline or elevation of >3x ULN from the subject's actual baseline if not normal, and total bilirubin >2x ULN or INR >1.5.

If any of the above criteria is met by a Part B or Part D subject who has not completed dosing with IP, treatment must be interrupted immediately and the Medical Monitor notified of this action.

A thorough investigation of other potential causes should be conducted in all cases. If no convincing alternative etiology (eg, pre-existing CF-related liver disease, viral hepatitis, alcohol ingestion, concomitant medication [such as antibiotic treatment]) for the elevated transaminases and symptoms is identified, regardless of whether ALT or AST levels have improved, treatment of the subject must be discontinued, in consultation with the Medical Monitor. If a convincing alternative etiology for the elevated transaminases is identified and the subject's symptoms and laboratory findings have improved, the Investigator may consider resuming IP treatment with close monitoring, in consultation with the Medical Monitor.

The reason for withdrawal must be determined by the Investigator and recorded in the subject's medical record and on the CRF. If a subject is withdrawn for more than 1 reason, each reason should be documented in the source document and the most clinically relevant reason should be entered on the CRF.

Reasons for discontinuation include but are not limited to:

- AE
- Pregnancy
- Protocol deviation
- Withdrawal by subject
- Lost to follow-up
- Physician decision
- Study terminated by Sponsor
- Other (if "Other" is selected, the Investigator must specify on the CRF)

For all discontinued subjects who received the IP, every attempt must be made to follow each subject for the duration of the study.

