- k Subjects should be randomized following confirmation of eligibility on Day 1. Confirmation of eligibility on Day 1 requires a review of the Day -1 results and pre-dose Day 1 results of physical exam, AE, conmeds, vital signs and pulse oximetry. A subject is considered enrolled into the study when he or she has been randomized.

- 1 An electrocardiogram will be performed pre-dose on dosing Day 15; and pre-dose and 6 hours after treatment on dosing Day 29.
m Subjects will be in a fasted state (8hrs without food or drink except water) for serum chemistry study blood collections.

Table 8: Part D - Schedule of Procedures for Screening through Day 18

Study Day	Screening Period Day -28 to -1	Treatment Period										Follow-Up Period		
		Day 1 ^a		Day 2		Day 3		Day 4		Day 5		Day 8 (±1 day)	Day 11 (±1 day)	Day 18 (±1 day)
		Pre-Dose	2 hours post-dose	Pre-Dose	2 hours post-dose	Pre-Dose	2 hours post-dose	Pre-Dose	2 hours post-dose	Pre-Dose	2 hours post-dose			
Clinic visit (outpatient) ^a	X	X	X	X	X	X	X	X	X	X	X		X	X
Telephone contact													X	
Informed consent	X													
Inclusion/exclusion criteria	X	X												
Demography and medical/medication history	X													
Full Physical examination	X												X	X
Limited physical exam		X	X	X	X	X	X	X	X	X	X			
Vital signs (BP, HR, body temperature, RR) ^b	X	X	X	X	X	X	X	X	X	X	X		X	X
Pulse oximetry	X	X	X	X	X	X	X	X	X	X	X		X	X
Height ^c	X													
Weight	X													
Serum chemistry, hematology, coagulation, urinalysis, CRP	X	X				X				X			X	X
Serum inflammatory markers ^h		X		X		X		X		X			X	X
Serum or urine pregnancy test ^d	X	X												
Drug and alcohol screening	X													
Spirometry ^e	X	X	X	X		X		X		X			X	X

Table 8: Part D - Schedule of Procedures for Screening through Day 18														
Study Day	Screening Period Day -28 to -1	Treatment Period										Follow-Up Period		
		Day 1 ^a		Day 2		Day 3		Day 4		Day 5		Day 8 (±1 day)	Day 11 (±1 day)	Day 18 (±1 day)
		Pre-Dose	2 hours post-dose	Pre-Dose	2 hours post-dose	Pre-Dose	2 hours post-dose	Pre-Dose	2 hours post-dose	Pre-Dose	2 hours post-dose			
Viral screening (HIV, HBV, HCV)	X													
Chest x-ray ^f	X												X	
Electrocardiogram (ECG)	X											X		
█ mRNA and █ assays ^h		X	X	X	X	X	X	X	X	X	X		X	X
Immune response assays ^{g,h}		X											X	X
Adverse event collection	X	X	X	X	X	X	X	X	X	X	X	X	X	X
Concomitant medication collection	X	X	X	X	X	X	X	X	X	X	X	X	X	X
Concomitant surgical procedure collection	X	X	X	X	X	X	X	X	X	X	X	X	X	X

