4.5.6. Study Stopping Criteria

IP administration will be halted for all subjects if any of the following stopping criteria are met:

- a. A subject experiences a Grade 4, life-threatening treatment-emergent AE or death that is considered probably or definitely related to IP by the Investigator
- b. Two or more subjects in a dose group experience 1 or more moderate or severe pulmonary exacerbations during the 5-week treatment period in Part B or through Day 11 (1 week post-5th dose) in Part D
- c. Two or more subjects in a dose group experience an absolute decrease in predicted FEV1 of at least 25 % compared to the baseline value (defined as the average of the Day -1 and Day 1 pre-dose values) during the 5-week treatment period in Part B or through Day 11 (1 week post-5th dose) in Part D that cannot be explained, in the opinion of the Investigator, by the underlying disease of CF and that is confirmed on 2 separate occasions at least 3 days apart
- d. Two or more subjects in the study experience a suspected serious allergic/hypersensitivity reaction, including but not limited to anaphylaxis, generalized rash or bronchospasm likely to be related to drug treatment
- e. Two or more subjects in a dose group experience a deterioration in liver function, as detailed below:
 - i. Elevation of ALT or AST to >5 x ULN in a subject regardless of baseline value
 - ii. Elevation of ALT or AST to >3 x ULN in a subject with a normal baseline or elevation of >3 x ULN from the subject's actual baseline if not normal, with the

appearance of fatigue, nausea, vomiting, right upper quadrant pain or tenderness, fever, rash, and/or eosinophilia (>5%).

- iii. Elevation of ALT or AST to >3x ULN in a subject with a normal baseline or elevation of >3x ULN from the subject's actual baseline if not normal, and total bilirubin >2x ULN or INR >1.5.

To determine whether these stopping rules have been met, all available data relating to the safety of the IP will be reviewed by the PSRC. The treatment assignment of one or more subjects may be unblinded at the request of the PSRC, as described in Section 3.4.1.2. Following this review, the PSRC will decide if the study will:

- Resume unchanged or
- Resume with modifications to the protocol or
- Be terminated.

The Sponsor is responsible for notifying the relevant regulatory authorities and the Investigator is responsible for promptly notifying the relevant IRB of the decision.

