7.3.1.2. Rescreening of Subjects

Rescreening of subjects, as described in Section [7.1.1.2](#) for Part A, also applies to Part D.

7.3.2. Treatment Period: Day 1 to Day 5

See [Table 8](#) for the Schedule of Procedures for the treatment period of Part D.

Following screening, eligible subjects will return to the study center on Day 1 and will perform the baseline procedures and tests, as described in [Table 8](#).

Pre-dose assessments on Day 1 should be performed prior to IP administration; these assessments include a pregnancy test (female subjects only), collection of blood for safety labs, limited physical examination, measurement of vital signs and oxygen saturation (pulse oximetry), and spirometry testing. If the subject is receiving treatment with an inhaled short-acting bronchodilator as part of their routine pulmonary therapies (see below), pre-dose spirometry testing may be scheduled before the subject's pulmonary therapies (if the subject's schedule permits) so that it can be performed "pre-bronchodilator." Alternatively, the subject may choose to delay the bronchodilator treatment until after the pre-dose spirometry testing is performed and receive the treatment just prior to the administration of IP, as described below. Recording of any AEs and concomitant medications should continue at this time. The only procedures and tests performed pre-dose on Day 1 that will be used to confirm eligibility are the limited physical exam, vital signs, pregnancy test, and pulse oximetry; these results will only be exclusionary for subjects if there is a clinically significant or relevant change in a result, as determined by the Investigator (eg, positive pregnancy test).

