Prior to IP administration, subjects should undergo their routine pulmonary therapies (airway clearance and pulmonary medications). These may be administered either at home or at the study center and may include but are not limited to chest physiotherapy, and treatment with inhaled bronchodilators, hypertonic saline, antibiotics, and steroids (Section [5.1.1](#)). The administration of IP should optimally occur within 2 to 3 hours after subjects have completed their pulmonary therapies for the day. For subjects whose routine pulmonary medications do not include an inhaled short-acting beta-agonist (or it is not given within the 2 to 3 hour window prior to IP administration), albuterol (2 to 4 puffs) will be administered via metered-dose inhaler approximately 20 minutes before treatment with IP to minimize any potential bronchoconstrictive effects (Section [5.1.1](#)). Note that administration of a short-acting beta-agonist via nebulization is also permitted at the discretion of the Investigator

Following confirmation of eligibility, subjects will be randomized to receive the first dose of either MRT5005 or placebo (subjects who are randomized are considered enrolled into the study). The administration of IP will be performed by a blinded, qualified member of the study staff. IP will be administered by the respiratory route using an InnoSpire Go nebulizer.

Nebulization time is expected to be approximately 22 minutes or less. See Section [6.2.2](#) for details on the preparation and dosing of IP, which includes minimizing secondary exposure to study staff during nebulization of IP.

The second through fifth doses of IP will be administered on Days 2, 3, 4, and 5, respectively. Pre-dose assessments will occur on each dosing day (as noted in [Table 8](#)) and IP should continue to be administered within 2 to 3 hours after subjects have completed their routine pulmonary therapies.

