7.5.2.12. Spirometry

Spirometry will be performed according to the guidelines published by the American Thoracic Society for standardization of spirometry (American Thoracic Society 1995). The following parameters will be assessed during the spirometry testing:

- Forced expiratory volume in 1 second (FEV₁): absolute volume (L) and percent predicted for age, gender, and height.
- Forced vital capacity (FVC): absolute volume (L) and percent predicted for age, gender, and height.
- FEV₁/FVC: ratio and percent predicted for age, gender, and height.
- Forced expiratory flow over the middle one-half of the FVC (FEF_{25-75%}): absolute volume (L) and percent predicted for age, gender, and height.

The parameters will be normalized using the ERS Global Lung Function Initiative (GLI) prediction equations.³³ The average of the results from the testing on Day -1 and at pre-dose on Day 1 will serve as the subject's baseline for Parts A and B. The average of the results from the testing on Screening and at pre-dose on Day 1 will serve as the subject's baseline for Part D.

Instructions on Bronchodilator Use in Relation to Spirometry Testing

- If feasible for the subject, all spirometry testing should be performed "pre-bronchodilator" if the subject is receiving treatment with a short-acting beta-agonist or anticholinergic bronchodilator (eg, beta-agonist medication such as albuterol or anticholinergic agent such as ipratropium bromide). These medications should be withheld for at least 4 hours before spirometry testing.
- If the subject is receiving treatment with a long-acting bronchodilator (eg, salmeterol), these medications do not have to be withheld and spirometry testing can be performed at any time in relation to dosing with the long-acting bronchodilator.

Instructions on Subject's Routine Pulmonary Therapies in Relation to Spirometry Testing

- For testing consistency within a subject, it is suggested that all spirometry testing for a subject be consistently performed either before or after receiving their daily routine pulmonary therapies (airway clearance and pulmonary medications). It will be at the discretion of the Investigator and study staff to determine what is most feasible for each subject and to maintain this testing consistency throughout the study.

If a subject is experiencing respiratory distress or respiratory symptoms, based on the judgment of the Investigator, unscheduled spirometry testing may be performed when the subject is stable.

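### Part D: the individual FEV1 stopping rule needs confirmation at least 3 days apart while doses are daily, with no mandatory hold, so a fall first seen pre-dose on Day 3, 4 or 5 spares no dose under that rule

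*Protocol*

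**What the plan says.** Protocol 4.5.1, rule 2, applies through the 5-week treatment period in Part B and through Day 11 in Part D. It needs an absolute fall of at least 25% in predicted FEV1 (read here as 25 points of ppFEV1) that the Investigator cannot attribute to CF. The fall counts only when it is repeated: "by the underlying disease of CF and that is confirmed on 2 separate occasions at least 3 days apart". The reference value is "defined as the average of the Day -1 and Day 1 pre-dose values".

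Section 4.5.1 also orders immediate interruption when a criterion is met by a Part B or Part D subject who is still being dosed. For FEV1, confirmation is part of the criterion, so that order does not apply at the first fall.

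For Part D, section 7.3.2 states: "The second through fifth doses of IP will be administered on Days 2, 3, 4, and 5, respectively". Table 8 places spirometry at Screening, Day 1 pre-dose and 2 hours post-dose, pre-dose on Days 2 to 5, and then Days 11 and 18. Section 7.5.2.12 sets the Part D spirometry baseline differently from the rule: "The average of the results from the testing on Screening and at pre-dose on Day 1".

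Study criterion 4.5.6(c) uses the same fall, interval and baseline for two or more subjects in a dose group, "during the 5-week treatment period in Part B or through Day 11 (1 week post-5th dose) in Part D". Its consequence is wider: "IP administration will be halted for all subjects if any of the following stopping criteria are met".

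**The concern.** The interval works with weekly dosing, but the rule also names Part D, where all five doses fall within five days. A subject can show a qualifying fall on a scheduled pre-dose test and still be given the remaining doses, because the rule cannot act until at least 3 days later.

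Safety and tolerability is the primary objective, and section 2.2.3 assumes the lung is the main site of any adverse effect. A mandatory lung-function rule that cannot act for falls first seen on three of the five dosing days gives less protection than a reader would suppose. Part D is also unstaggered (3.2.3), so 4.5.6(c) may act after some Part D subjects have finished dosing.

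The baseline adds a smaller difficulty. The rule calls for a Day -1 value, but Table 8 has no Day -1 visit.

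**Working it through.** The plan states no figure to reproduce. This is a day count.

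Inputs: doses on Days 1 to 5 at 4 mg (7.3.2); spirometry days from Table 8; interval of at least 3 days (4.5.1, rule 2).

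Earliest confirmation day = day first seen + 3, with unscheduled tests allowed. Doses spared = doses due on or after that day. Base case: two tests in all, calendar days, and the confirming test done and read before that day's dose.

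| First seen | Earliest confirmation | Doses still given | Doses spared |
|---|---|---|---|
| Day 1, 2 h | Day 4 | 2, 3 (8 mg) | 4, 5 |
| Day 2 pre-dose | Day 5 | 2, 3, 4 (12 mg) | 5 |
| Day 3 pre-dose | Day 6 | 3, 4, 5 (12 mg) | none |
| Day 4 pre-dose | Day 7 | 4, 5 (8 mg) | none |
| Day 5 pre-dose | Day 8 | 5 (4 mg) | none |

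Other readings:

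- Scheduled tests only: a fall first seen on Day 3, 4 or 5 is next tested on Day 11, which is 11 − 5 = 6 days after the last dose.
- Confirming test not read before that day's dose: the Day 1 case spares dose 5 only and the Day 2 case spares none. Doses 2 to 5 then follow the Day 2 fall: 4 × 4 = 16 mg.
- Strict 72 hours, same clock time daily, 22-minute nebulization: from the Day 1 2-hour test to Day 4 pre-dose is 72 − 2 − 22/60 = 69.6 h. The Day 1 case then spares dose 5 only. The maximum given stays at 3 doses.
- A first fall plus two further confirmations, the first of them next day: earliest day = day first seen + 1 + 3. The Day 1 case reaches Day 5 and spares dose 5. The Day 2 case reaches Day 6, spares none, and 4 doses (16 mg) follow.
- Inclusive counting (Day 3 to Day 5 taken as 3 days): a Day 3 fall spares dose 5. Days 4 and 5 still spare none. This is not the plain meaning of the wording.

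Part B comparison: doses are 7 days apart and 7 ≥ 3, so the next pre-dose test can confirm. If it is read before dosing, at most 1 dose follows a first fall; if not, 2. Table 7 footnote j requires spirometry review before the first dose only, so the lower figure is also an assumption.

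Part D baseline, three definitions:

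- Rule 4.5.1(2) and 4.5.6(c): mean of Day -1 and Day 1 pre-dose.
- Protocol 7.5.2.12: mean of Screening and Day 1 pre-dose.
- SAP Section 3 and footnote RE_F01D: Day 1 pre-dose alone.

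The last two differ by half the Screening-to-Day-1 difference: (S + D)/2 − D = (S − D)/2.

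**The case against.** The strongest reply is that rule 2 is not the only brake. The Investigator or Sponsor may withdraw a subject at any time (4.5). A spirometry change judged clinically significant is an AE (8.1.4), and an AE or a physician decision is a listed reason to discontinue (4.5.1). Rule 3 stops a subject at one suspected moderate to severe hypersensitivity reaction, including bronchospasm, without confirmation; it was broadened in the amendment that added Part D. A subject with a safety concern at 2 hours stays on site (7.3.2). The PSRC and Sponsor may end treatment or lower the dose (3.2.3). Part D time windows are not obligatory (7.3), so a site has room to delay. On this view rule 3 covers acute airway events and rule 2 covers sustained decline. Total exposure is capped at 20 mg, which section 2.2.3 relates to the 20 mg single dose.

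Most of this stands, and it limits the point. A reader might infer that nothing can stop dosing after a first fall; the documents do not support that, because only a mandatory hold is missing. But each alternative needs a judgement or a separate event, and a fall found on spirometry alone triggers none of them automatically.

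One piece of supporting text is weaker than it looks. Section 7.3.2 says "The only procedures and tests performed pre-dose on Day 1 that will be used to confirm eligibility are the limited physical exam", and goes on to list other checks without spirometry. That sentence concerns Day 1 eligibility, and the Day 1 pre-dose test is part of the baseline, so it cannot show a fall. The relevant gap is that no Part D text requires spirometry to be read before doses 2 to 5.

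**Conclusion.** The point holds for Part D and is worth amending. Under rule 4.5.1(2), a fall first seen pre-dose on Day 3, 4 or 5 spares no dose. One first seen at the Day 1 2-hour test spares at most 2 doses, and one first seen pre-dose on Day 2 at most 1. At most 3 doses (12 mg) follow a first fall, assuming that two tests suffice and that the confirming test is read before dosing. Without either assumption the figure can reach 4 doses (16 mg).

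Two stronger readings should be resisted. The rule is not wholly inoperative in Part D, since early falls can still spare doses. Nor do the documents show that harm is likely: they give no frequency for such falls, and other controls exist. The baseline mismatch is a separate drafting fault that should be corrected at the same time; it does not make the timing problem larger.

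**What to change.** For Part D, amend 4.5.1(2) and 7.3.2 as follows:

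1. Review pre-dose spirometry before each dose on Days 2 to 5.
2. Hold dosing at the first unexplained absolute fall of at least 25 points in ppFEV1.
3. Repeat the test the next day. After a Day 5 fall this is an unscheduled test, which 7.5.2 permits.
4. Discontinue if the fall is confirmed, otherwise resume. State whether a held dose is skipped or made up.

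The liver rule in 8.1.4.1 already works this way: interrupt at the initial result, with repeat testing in 48 to 72 hours.

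Set one Part D baseline in 4.5.1(2) and 4.5.6(c), and align it with 7.5.2.12, SAP Section 3 and RE_F01D. Add the word absolute to SAP 2.7(c), which omits it. Leave the 3-day confirmation in 4.5.6(c) to the sponsor: shortening it trades specificity for speed in a rule that halts dosing for everyone.

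The cost is wording and no new scheduled visit, apart from a Day 6 visit if a dose is made up after a Day 5 hold. A noisy test may delay or cost a dose. One skipped dose leaves 5 − 1 = 4 within 5 days, which still meets the dosing part of Part D evaluability in SAP 2.3. Two skipped doses leave 3, which does not. Next-day confirmation also shows a less sustained fall than the present interval.

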 - Abnormal liver function defined as meeting any 3 or more of the following: ALT $>3x$ upper limit of normal (ULN); AST $>3x$ ULN; GGT $>2.5x$ ULN; alkaline phosphatase $>2.5x$ ULN; and total bilirubin $>1.5x$ ULN (except for patients with isolated Gilbert Syndrome).

8. Any clinically significant abnormal laboratory test result prior to Day 1 that would interfere with the study assessments or indicate clinical instability of the patient, as judged by the Investigator.
9. Infection with highly virulent bacteria associated with accelerated decline in pulmonary function and/or decreased survival (eg, *Burkholderia cenocepacia*, *Burkholderia dolosa*, *Mycobacterium abscessus*). For a patient with a history of positive culture, he/she can be considered free of infection based on the following guidance:
 - All cultures obtained within the past 12 months should be negative for these bacteria. The patient should have had at least 2 cultures performed within the past 12 months, at least 3 months apart, with at least 1 culture obtained within 6 months of screening for this study.
10. History of or listed for solid organ or hematological transplantation.
11. Positive viral serology test results for HIV type 1 or 2 antibodies, hepatitis B surface antigen (HBsAg), or hepatitis C virus (HCV) antibodies at screening.
12. Positive test for drugs of abuse or alcohol at the screening visit.
13. Donation of blood or blood products within 60 days prior to the initial screening visit.
14. Participation in an IP or device study within 30 days prior to the initial screening visit or at any time during this Translate Bio-Sponsored study. (The 30-day window applies to IPs with elimination half-lives of <6 days. If the elimination half-life of the IP is \geq 6 days, then the window should be extended to at least 5 half-lives from the last dose administered.)
15. Prior enrollment in this study, with the exception of subjects who discontinued treatment after one dose of study drug for a reason unrelated to safety as specified in Section [7.1.1.2](#). (A patient is considered enrolled into the study when he or she has been randomized.)
16. Any suspicion of, or history of, alcohol and/or other substance abuse or addiction within the past year.
17. Pregnant or lactating females.

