8.1.4.1. Evaluation of Elevations in Liver Function Tests

Subjects meeting any of the 3 criteria listed below must be followed closely with repeat confirmatory testing within 48 to 72 hours of the initial finding (should include ALT, AST, ALP, GGT, INR, and total bilirubin testing) to determine if these parameters are increasing or decreasing. Subjects should be followed closely for clinical progression and there should be monitoring of ALT, AST, ALP, GGT, INR, and total bilirubin levels, as clinically indicated. Subjects should be followed until their transaminases and other laboratory parameters normalize or return to baseline.

- Elevation of ALT or AST to >5 x ULN in a subject regardless of baseline value
- Elevation of ALT or AST to >3 x ULN in a subject with a normal baseline or elevation of >3 x ULN from the subject's actual baseline if not normal, with the appearance of fatigue, nausea, vomiting, right upper quadrant pain or tenderness, fever, rash, and/or eosinophilia ($>5\%$).
- Elevation of ALT or AST to >3 x ULN in a subject with a normal baseline or elevation of >3 x ULN from the subject's actual baseline if not normal, and total bilirubin >2 x ULN or INR >1.5 .

If any of the above criteria is met by a Part B or Part D subject who has not completed dosing with IP, treatment must be interrupted immediately and the Medical Monitor notified of this action.

A thorough investigation of other potential causes should be conducted in all cases. If no convincing alternative etiology (eg, pre-existing CF-related liver disease, viral hepatitis, alcohol ingestion, concomitant medication [such as antibiotic treatment]) for the elevated transaminases and symptoms is identified, regardless of whether ALT or AST levels have improved, treatment of the subject must be discontinued, in consultation with the Medical Monitor. If a convincing alternative etiology for the elevated transaminases is identified and the subject's symptoms and laboratory findings have improved, the Investigator may consider resuming IP treatment with close monitoring, in consultation with the Medical Monitor.

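### When ALT and AST are both at or above 2x ULN at baseline, raised bilirubin or INR adds no liver trigger beyond the 5x ULN rule

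*Protocol*

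**What the plan says.** Protocol Section 4.5.1, rule 4, has three limbs. Limb (a) is ALT or AST above 5x ULN "in a subject regardless of baseline value". Limbs (b) and (c) share an enzyme condition: above 3x ULN if the baseline is normal, or a rise of more than 3x ULN from the subject's own baseline if it is not. Limb (b) adds symptoms, fever, rash or eosinophilia. Limb (c) adds bilirubin or INR; its abnormal-baseline part reads "elevation of >3x ULN from the subject's actual baseline if not normal, and total bilirubin >2x ULN or INR >1.5".

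Three consequences hang on these limbs:

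- **Interruption (4.5.1).** For a Part B or Part D subject "who has not completed dosing with IP, treatment must be interrupted immediately".
- **Retest (8.1.4.1).** "Subjects meeting any of the 3 criteria listed below must be followed closely with repeat confirmatory testing within 48 to 72 hours".
- **Study halt (4.5.6(e)).** Dosing is halted for review when "Two or more subjects in a dose group experience a deterioration in liver function". Item (iii) repeats limb (c), including "from the subject's actual baseline if not normal, and total bilirubin >2x ULN or INR >1.5".

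SAP Section 2.7 carries the same wording. On entry, exclusion 7 in Section 4.2 reads "Abnormal liver function defined as meeting any 3 or more of the following": ALT >3x, AST >3x, GGT >2.5x, alkaline phosphatase >2.5x, or total bilirubin >1.5x ULN.

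**The concern.** A transaminase rise together with raised bilirubin or INR is more worrying than the same rise alone, and limb (c) exists to act on it below 5x ULN. For a subject who enters with both enzymes clearly raised, the clause written for abnormal baselines looks unable to do so.

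If that is right, enzymes moving into the range of 3x to 5x ULN with bilirubin above 2x ULN or INR above 1.5 would bring no mandatory interruption, no mandatory retest and no count toward halt (e). A subject with a normal baseline and the same on-study values would meet limb (c).

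**Working it through.** **Thresholds.** All values are in multiples of ULN, and b is the baseline of both enzymes. Limb (a) needs a value > 5. The abnormal-baseline part of (c), read as written, needs a value > b + 3. It lies wholly inside (a) when b + 3 ≥ 5, that is, b ≥ 2. If the clause is read instead as three times baseline, it needs > 3b, which lies inside (a) when b ≥ 5/3.

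| b | (c) as written: above b + 3 | (c) as three times baseline: above 3b | Room for (c), as written, below (a) | Room with a 1x ULN margin: 5 − max(3, b + 1) |
|---|---|---|---|---|
| 1.5 | 4.5 | 4.5 | 0.5 | 2.0 |
| 1.9 | 4.9 | 5.7 | 0.1 | 2.0 |
| 2.0 | 5.0 | 6.0 | 0 | 2.0 |
| 2.5 | 5.5 | 7.5 | 0 | 1.5 |
| 3.0 | 6.0 | 9.0 | 0 | 1.0 |
| 3.5 | 6.5 | 10.5 | 0 | 0.5 |

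A third reading, above 3x ULN from any baseline, would remove the problem. It is less natural: the text uses *to* for a normal baseline and *of … from* otherwise, and this reading would make that split pointless.

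**Grid check.** Take on-study ALT/AST pairs in steps of 0.1, neither below its baseline, with at least one above 3 and neither above 5. At baseline 2.5/2.5 there are 26² − 6² = 640 such pairs. Limb (c) as written covers 0. With a 1x ULN margin (value ≥ 3.5) it covers 26² − 10² = 576. These are coverage counts, not probabilities.

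**Example.** ALT and AST are both 2.5 at baseline, then both 4.0 with bilirubin 3x ULN and INR 1.6. Limb (a) needs > 5 and (c) needs > 5.5, so neither is met. With a 1x ULN margin, (c) is met.

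**Eligibility.** ALT and AST both at 2.0 or 2.5, other tests normal, give 0 of 5 flags; both at 3.5 give 2 of 5. Exclusion 7 needs 3, so it removes none of these.

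**When it could matter.** The schedules (Tables 1 to 9) and the sample counts in Appendix 4 agree on chemistry and coagulation draws:

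- Part A: 9 draws, 7 after dosing.
- Part B: 11 draws, 9 after the first dose. Those before the last dose are pre-dose Days 15 and 29, with 3 and 1 doses left.
- Part D: 11 draws, 9 after the first dose. Those before the last dose are pre-dose Days 3 and 5, with 3 and 1 doses left.

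Part A gives one dose, so interruption cannot arise there. Section 12 of the protocol names the remaining subjects under version 5.0 as Part B 12 mg, Part B 20 mg and Part D: 4 + 4 + 8 = 16 planned, of whom 3 + 3 + 6 = 12 are on active drug.

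**Reporting.** SAP Section 9.5 summarizes chemistry and hematology only, and Listing 16.2.8.4 gives coagulation for Parts B and D only. Part A's 16 × 7 = 112 scheduled post-dose INR values appear in no planned table, figure or listing.

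**The case against.** The strongest reply is that redundancy is not absence of protection. Limb (a) needs no bilirubin, INR or symptom, and from a baseline of 2.5x ULN it fires on a rise above 2.5x ULN. Letting a fixed cap govern abnormal baselines is a coherent choice in CF, where Section 4.5.1 itself names pre-existing liver disease as an alternative cause.

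Other safeguards exist:

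- Exclusions 1 and 8 let the Investigator keep out clinically significant liver disease or laboratory abnormalities.
- Worsening of an already abnormal value can be an AE (8.1.4), and AEs are followed to closure (8.1).
- The PSRC hears of related SAEs in real time and receives SAE listings after each dose group (3.4.1.2).
- The Investigator or Sponsor may withdraw a subject at any time (4.5).

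The timing also narrows the point. Part B pre-dose tests come immediately before dosing, and no requirement was found to review chemistry first. If the result arrives after that day's dose, the Day 29 and Day 5 draws prevent nothing.

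All of this stands and limits the size of the problem. It does not restore limb (c): none of these safeguards is triggered by the joint enzyme and bilirubin or INR finding. The scheduled PSRC review in Part B is tied to Groups 1 and 2 (3.4.2), and none is named for the 12 mg and 20 mg groups or Part D.

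Two further objections are accepted. A 1x ULN margin has no source in the documents. Applied to every abnormal baseline, it would also lower (c) between 1x and 2x ULN, where no redundancy is claimed: at 1.5/1.5, coverage would go from 335 to all 1,040 mid-range pairs. The missing Part A coagulation listing is a separate reporting gap, included because INR is one of the two alternative conditions in (c).

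**Conclusion.** The point holds for subjects whose ALT and AST are both at least 2x ULN at baseline. For them limb (c) is contained in limb (a) on both natural readings, in 4.5.1, 4.5.6(e)(iii), 8.1.4.1 and SAP 2.7. It rests on taking *elevation from baseline* as a difference or a multiple. If the sponsor meant *above 3x ULN from any baseline*, the text needs correcting to say so.

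The practical effect is probably small. The number of such subjects is not in the documents, dosing decisions are affected only for those still to be dosed, and at most two draws per part come before the last dose.

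Three stronger readings are not supported:

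- A reader might infer that subjects with raised baseline enzymes have no liver stopping rule. They do: limb (a) applies to them without conditions.
- A reader might infer that the abnormal-baseline clause never works. As written it can still act when either enzyme is below 2x ULN at baseline, though with little room just under that value (0.1x ULN at 1.9).
- A reader might infer that every post-dose draw in all three parts carries a lost dosing decision. Most draws follow the last dose; there only the retest and the halt count could be affected, and a halt matters only while someone is still being dosed.

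**What to change.** 1. **SAP flag.** Flag any post-baseline ALT or AST above 3x ULN with same-visit total bilirubin above 2x ULN or INR above 1.5, whatever the baseline, and show baseline values beside it. This is one derived variable from data already collected. It would use the global reference ranges in the listings, so it may differ from a site's judgment on local ranges.

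2. **Part A coagulation.** Extend Listing 16.2.8.4 to Part A. The cost is one added listing.

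3. **Limb (c), for subjects still to be dosed.** Reword the abnormal-baseline part so that it can act below 5x ULN. For example: ALT or AST above 3x ULN and above that enzyme's own baseline by a margin set by the sponsor's medical team, with the bilirubin or INR condition unchanged. A margin of 1x ULN is one option; it adds essentially nothing to (a) from a baseline of 4x ULN upward. If the sponsor does not want a lower trigger for baselines of 1x to 2x ULN, restrict the new wording to baselines of 2x ULN or more. That leaves a step: a baseline of 1.9 would need > 4.9x ULN, while 2.0 would need > 3.0x ULN.

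Item 3 needs a protocol amendment in three sections with IRB approval, plus matching text in SAP 2.7 and the PSRC charter. Its downside is a few more interruptions, or counts toward halt (e), in subjects with pre-existing CF liver disease or Gilbert syndrome; a subject already above 2x ULN for bilirubin meets that half of (c) throughout. Section 4.5.1 already lets the Investigator consider resuming: "If a convincing alternative etiology for the elevated transaminases is identified and the subject's symptoms and laboratory findings have improved".

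Leave limb (b) unchanged, although its enzyme clause has the same redundancy. Fever is expected here (7 febrile reactions are reported in Section 2.2.3), and a lower limb (b) could trip halt (e) on fever with a modest ALT rise.
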